2.3 Global Good/Intellectual Ventures Pediatric Mask (Nasal Reservoir Cannula)

Improving oxygen delivery and extending oxygen supplies to ill patients with respiratory distress can reduce fatalities in resource-poor settings. Global Good has developed a low cost oxygen mask (nasal reservoir cannula) to more efficiently deliver oxygen to the pediatric patient by increasing dead space to recapture a portion of expelled oxygen using

¹ Efficiency gain is based on adult patients. Most conserving devices are not approved for pediatric use.

[figure not shown]
the spatial distribution of the nasal reservoir cannula volume and length of surface seal. This nasal reservoir cannula fits over a standard nasal cannula (also termed prong) (see Fig. 1 below). The system is designed to reduce administered oxygen to deliver an equal or higher fraction of inspired oxygen (FiO₂) per oxygen delivered (L/min) compared with a standard nasal cannula alone. Please refer to the device brochure (Appendix I) for instructional details on the nasal reservoir cannula.

Figure 1. Novel Nasal Reservoir Cannula

[figure not shown]
Mask performance was evaluated using a breathing simulator developed at the Global Good Laboratory (Bellevue, WA). The system consists of a breathing simulator (ASL 5000, IngMar Medical, Pittsburgh, PA) paired with an anatomically correct airway and face constructed by 3D printing computerized tomography scan data (Fig. 2). Carbon dioxide was titrated into the lung to simulate metabolism. The end-tidal carbon dioxide (CO₂), which is equivalent to the maximal concentration of carbon dioxide at the end of an exhaled breath, and FiO₂ were measured. An array of breathing waveforms was tested to bound mask performance.

Figure 2. Pediatric Breathing Simulator

For hospitalized patients with hypoxic respiratory illnesses, the minimal oxygen delivered recommended by the World Health Organization (WHO) is in ranges typically used in low-flow nasal cannulas; in vitro experiments on the breathing simulator indicate that the novel nasal reservoir cannula may be able to provide the same or higher FiO₂ at approximately 2.5-times lower oxygen flow rate (L/min) compared with a standard nasal cannula alone (Global Good, data on file; see Fig. 3). This can result in less oxygen used than conventional delivery systems, which may be valuable for resource limited settings where oxygen supplies are limited.

Figure 3 Oxygen Flow and FiO₂ of Novel Mask (Nasal Reservoir Cannula)

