4.2.2 Investigational Treatment Periods

4.2.2.1 Period 1

Patients will be placed on supplemental oxygen consistent with standard of care.

(Group A): Nasal Reservoir plus Nasal Cannula (1 hr duration) (Group B): Nasal Cannula (1 hr duration)

- Continuous monitoring of peripheral blood oxygen saturation (by pulse oximetry) with recordings every 15 min.
- Continuous end-tidal carbon dioxide (CO₂) monitoring with recordings every 15 min.
- Record vital signs every 15 min.
- Record oxygen flow (L/min) every 15 min.
- Record concomitant medication information.
- Record adverse event information.
- Physical examination, including capillary refill time; capillary blood gases (PaO₂, PaCO₂, pH, base excess, lactate); and completion of SICK score form at end of Period 1.

4.2.2.2 Period 2

(Group A): Nasal Cannula Alone (1 hr duration)

(Group B): Nasal Reservoir and Cannula Alone (1 hr duration)

- Continuous monitoring of peripheral blood oxygen saturation (by pulse oximetry) with recordings every 15 min.
- Continuous end-tidal carbon dioxide (CO₂) monitoring with recordings every 15 min.
- Record vital signs every 15 min.
- Record oxygen flow (L/min) every 15 min.
- Physical examination, including capillary refill time; capillary blood gases (PaO₂, PaCO₂, pH, base excess, lactate); and completion of SICK score form *at end of Period* 2.

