10.3 Safety Variables

Safety evaluations will include collection of adverse event, physical examination, vital sign, and clinical laboratory data. Hemoglobin rapid test, malaria rapid test, and blood glucose (point of care) will be obtained along with complete blood count (CBC), which may include hemoglobin, hematocrit, erythrocyte or red blood cell count (RBC), mean cell volume (MCV), segmented neutrophils, juvenile neutrophils, lymphocytes, monocytes, eosinophils, basophils, platelets, cell morphology, reticulocyte count.

Metabolic panel will be done based on local standard of care for patients with respiratory distress, but may include evaluation of

• Metabolic panel: Serum concentrations of sodium, potassium, chloride, total bilirubin, alkaline phosphatase, alanine transaminase (ALT), aspartate transaminase (AST), blood urea nitrogen (BUN), creatinine, glucose, total protein, albumin.

Safety evaluation will also involve the collection of data from: continuous transdermal endtidal carbon dioxide (CO₂) monitoring, capillary blood gases (P_aO₂, P_aCO₂, pH, base excess), peripheral blood oxygen saturation (SpO₂), and blood lactate.

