10.4 Oxygen Cylinder Use and Flow

The amount of oxygen (L) used from a cylinder and average oxygen flow (L/min) during Period 1 through 2 will be collected or calculated.

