10.5 Statistical and Analytical Plans

10.5.1 General Considerations

The full analysis population will include all randomly assigned subjects who have received study treatment. All variables will be summarized by descriptive statistics for each treatment group. The statistics for continuous variables will include mean, median, standard deviation, and number of observations. Categorical variables will be tabulated using frequencies and percentages.

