APPENDIX I DEVICE BROCHURE:

Global Good/ Intellectual Ventures Mask (Nasal Reservoir Cannula)

Rationale:

Used properly this oxygen conserving nasal reservoir cannula will provide the patient adequate oxygen support equal to that of with conventional nasal cannula with prongs and the following added benefits:

- It will take a lower oxygen flow rate (l/min) to provide the same level of oxygenation in the body, which can be as much as 50% less (depending on the actual flow rate) than that of with a standard nasal cannula
- In case of using an oxygen storage system (e.g. oxygen cylinder), it will last significantly longer and in turn increase treatment capacity, spare resources with the same level and quality of care

Directions:

The mask is recommended for patients aged ≥ 1 year and ≤ 6 years with body weight of ≥ 8 kg and ≤ 26 kg. The proper mask size should be selected based on the patient's body weight (see table 1). Patients with a body weight of 8-13 kg should receive treatment with the small 30 ml mask and patients with a body weight of 14-26 kg should receive treatment with the large 50 ml mask.

The duration of the treatment and the oxygen flow rate should be based on the clinical judgment of the physician. This mask should only be implemented when the patient is monitored by adequate pulse oximetry and blood gas analysis tools.

Table 1. Mask size selection should be made based on patient weight.

Mask size	Child weight
Small (30 mL)	8-13 kg
Large (50 mL)	14-26g

Application:

- 1. Connect the standard nasal cannula to the oxygen source.
- 2. Turn on the oxygen and set flow rate (l/min).
- 3. Insert the mask over the conventional nasal cannula with prongs by installing the prongs into the respective slots of the mask.
- 4. Place the mask over the nose of the patient. The nasal piece does not need to tightly cover the nose but should rest loosely on the nose and the philtrum (upper lip) of the patient with the prongs extending into the nostrils.
- 5. Place the nasal cannula flexible tubing over the ears of the patient and then under the chin (per manufacturer's instructions). Slide the bola of the standard nasal cannula up toward the chin.

Cleaning:

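### The summaries fixed in the protocol do not show at what oxygen flow the mask-hour CO2 was measured, so unchanged CO2 could be read as informing safety at a reduced flow that few children may have had

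*Protocol*

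**What the plan says.** **Device.** Section 2.3 says the mask works "by increasing dead space to recapture a portion of expelled oxygen". Its volume is 30 or 50 mL, by body weight. Section 2.3 cites simulator work in which the same or higher FiO2 was reached at a flow about 2.5 times lower. The device brochure (Appendix I) puts the saving at up to 50%, depending on the flow.

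**Flow in the mask hour.** Section 4.2.2 has children on supplemental oxygen in line with standard care and asks staff to "Record oxygen flow (L/min) every 15 min". It gives no step or target for lowering flow on the mask. The brochure says: "The duration of the treatment and the oxygen flow rate should be based on the clinical judgment of the physician".

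**Summaries.** CO2 is listed under efficacy (10.2.2) and again under safety (10.3). Flow has its own section, 10.4, where litres used and "average oxygen flow (L/min) during Period 1 through 2 will be collected or calculated". The general rule in 10.5.1 is that "All variables will be summarized by descriptive statistics for each treatment group". Section 10.5.5 repeats the list of descriptive statistics, and 10.5.6 deals with adverse events and treatment duration. None of these sections relates CO2 to the flow at the time.

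**The concern.** The objective in section 3 is preliminary information on safety and efficiency, including effect sizes for a definitive trial. For this device the two belong together: the benefit is a lower flow, and the question that added dead space raises is what happens to CO2 at that flow. A mask-hour CO2 value recorded at an unreduced flow describes a setting in which no oxygen is saved.

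If CO2 and flow are reported only as separate group summaries, stable CO2 in some children and lower flow in others could be read as one favourable result that no single child showed. Appendix H makes such a reading easier, because it already describes hypercapnia and other potential risks as independent of the device. A definitive trial could then be planned on CO2 data that say little about the intended flow.

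**Working it through.** There is no stated figure to reproduce. The sample size of up to 20 (section 10.1) rests on precedent and has no inputs. The check is of what the written summaries can show.

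**1. Average flow over both periods.** Take a cannula flow of 2 L/min. This is an assumption, inside the 1-4 L/min that section 2.2 gives for older children. With two one-hour periods, the average is (mask-hour flow + cannula-hour flow) / 2.
- Flow not reduced on the mask: (2 + 2) / 2 = 2.0 L/min.
- Flow halved (the brochure's upper figure): (1 + 2) / 2 = 1.5 L/min.
- Flow 2.5 times lower (2 / 2.5 = 0.8): (0.8 + 2) / 2 = 1.4 L/min.

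A child kept at 1.4 L/min in both hours also averages 1.4 L/min. The two-period average therefore cannot tell a reduction on the mask from no reduction at a lower setting.

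**2. Summaries by treatment group.** Two readings are possible.
- *Groups A and B*, the only groups the protocol defines. With the 2.5-fold reduction and no period effect, Group A averages (0.8 + 2) / 2 = 1.4 and Group B averages (2 + 0.8) / 2 = 1.4, a difference of zero. A CO2 summary over both hours is pooled across devices in the same way.
- *Device in use.* Mask and cannula hours are then separated, but each variable is still summarised on its own. A mask-hour CO2 mean does not show which values came from children whose flow had been lowered.

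**3. What the loss could mean for a zero count.** If no hypercapnia is seen in n mask hours, the exact one-sided 95% upper limit is 1 − 0.05^(1/n).

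| Mask hours at the flow in question | Upper limit |
|---|---|
| 20 (all) | 13.9% |
| 10 | 25.9% |
| 5 | 45.1% |
| 3 | 63.2% |

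The subset sizes 10, 5 and 3 are assumptions, since the protocol gives no expected share of children with reduced flow.

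**4. Whether the data exist.** They do. Sections 4.2.2.1 and 4.2.2.2 ask for SpO2 and CO2 "monitoring with recordings every 15 min", and for flow at the same interval, in both periods. Leaving out the start of the hour, 60 / 15 = 4 paired readings per child per device, or up to 4 × 20 = 80 in mask hours. Capillary gases are taken once, at the end of each period, and can be set beside the last recorded flow.

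**The case against.** The best case against the point is that 10.5.1 is a generic descriptive rule. It does not exclude a joint display, and such displays are commonly left to a statistical analysis plan, which is not shown here. Sections 10.2 to 10.4 list variables and do not prescribe analyses. The study is descriptive, tests are exploratory, and there is no CO2 success criterion. Hypercapnia leads to stopping the device or withdrawing the child at whatever flow it occurs (6.2.1, 8.1.5, Appendix H), and data are reviewed after 10 participants.

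Much of this stands. The absence of a plot from the protocol would not be a finding by itself. What remains is the wording that is fixed: flow averaged across both periods, and summaries by a group that, as defined, mixes both devices. An analysis that follows those words does not show the flow behind the CO2. The individual stopping rules protect the child but do not describe CO2 at a given flow.

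A reader might go further and infer that normal CO2 will be reported as proof of safety at reduced flow. The documents do not support that: no such claim is planned. A reader might also infer that lower flow flushes the reservoir less and so raises CO2 by a calculable amount. The protocol states the dead space but not the flushing. Any washout figure would rest on assumed breathing values, with the flow ratio put in as an input, and the brochure describes a loose fit. No CO2 effect can be estimated from the documents.

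One objection bears on the remedy. Clinicians choose the flow, so it may follow the child's condition, and CO2 compared by achieved flow is open to confounding. With up to 20 children, fixed bands of flow ratio would also be sparse and their cut-offs arbitrary.

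**Conclusion.** The point holds in a limited form. The protocol describes a mask intended for lower flow, does not require lower flow in the mask hour, and fixes summaries that, taken literally, leave the flow behind the mask-hour CO2 unknown. Unchanged CO2 could then be read as informing safety at reduced flow when it does not.

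The size of any error cannot be given, because the protocol states no CO2 values, variability or expected flows. The zero-event limits (13.9% for 20 mask hours against 45.1% for 5) show only how much less is known if few hours ran at reduced flow, and they depend on the assumed split. The conclusion also rests on reading 10.4 and 10.5.1 as written. It is a weakness of reporting that can be repaired from planned data, and a cheap improvement worth making; it is not evidence that the mask retains CO2.

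**What to change.** Amend 10.4, 10.5.5 and 10.5.6 as follows.

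1. Summarise flow, CO2 and SpO2 separately for the mask hour and the cannula hour, in place of one average over both periods.
2. For each child, list and plot CO2 and SpO2 against the flow recorded at the same 15-minute point.
3. Show the within-child mask-minus-cannula differences in CO2 and SpO2 beside the within-child flow difference. Label them descriptive, because flow is chosen by clinicians and may follow the child's condition.
4. Report how many children had a lower flow on the mask than on the cannula, and limit any statement about CO2 to the mask flows observed.

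The sponsor should also reconcile the passages on intended flow reduction (2.3 and the brochure's rationale) with those that leave flow to standard care or clinical judgment (4.2.2.1 and the brochure's directions). No flow rule is proposed here.

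The cost is wording and a few displays; no new measurements, visits or patients are needed. The drawback is a narrower CO2 statement if few children had a reduced flow.

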10.5.2 Handling of Missing Data

Missing data will not be imputed.

10.5.3 Subject Disposition

Study subject disposition will be summarized by treatment group. Subjects who discontinued study drug prematurely or withdrew from the study will be summarized and listed, with reason for early termination/withdrawal.

10.5.4 Subject Characteristics

Demographic and other baseline characteristics will be summarized by treatment group.

10.5.5 Efficacy Analyses

Data will be summarized using descriptive statistics (number of patients, mean, median, standard deviation, minimum and maximum) for continuous variables and frequency and percentages of categorical variables. Tests of significance will be done only on an exploratory basis.

10.5.6 Safety Analyses

Treatment-emergent AEs are defined as AEs occurring after the first initiation of treatment until completion of treatment. Duration of treatment will be summarized by treatment group. The incidence of all reported AEs and treatment-related AEs will be tabulated by treatment group. AEs will be classified by system organ class and verbatim term.

AEs will be listed and summarized by treatment group, verbatim term, severity, seriousness, and relationship to study drug. In the event of multiple occurrences of the same AE with the same verbatim term in one subject, the AE will be counted once as the worst occurrence. The incidence of AEs will be tabulated by system organ class and

treatment group. AEs leading to premature discontinuation of study drug or withdrawal from the study will be summarized and listed in the same manner.

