8 ADVERSE EVENT REPORTING

8.1 Definition of Adverse Event

For purposes of this trial, an adverse event (AE) will be defined as **any** new unfavorable or unintended sign, symptom, or disease or change of an existing condition, which occurs during or after treatment, whether or not considered treatment-related. If clinically significant laboratory values lead to or are associated with clinical symptom(s), the diagnosis should be reported as an AE. Lack of treatment effect is not an adverse event in clinical trials because the purpose of the clinical trial is to establish (or evaluate for) a treatment effect.

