8.1.1 Reporting Procedures for All Adverse Events

The investigator remains responsible for following, through an appropriate health care option, AEs that are serious or that caused the subject to discontinue the study. The subject should be followed until the event is resolved or explained. Frequency of follow-up is left to the discretion of the investigator.

Adverse event information will be collected through the study period. The investigator is responsible for assessing and recording all AEs. Each AE will be recorded and classified for intensity, seriousness, and causality. All AEs either observed by the investigator or reported by the subject will be recorded regardless of causality. The investigator will follow the subject until an AE resolves or stabilizes.

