10 DATA ANALYSIS METHODS

10.1 Determination of Sample Size

The target sample sizes for this study (up to 20 patients) are consistent with feasibility studies for other clinical interventions (Billingham et al., 2013).

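### Section 10.5.6 counts adverse events by the investigator's own wording, so one event described in different words is split across term-level rows and a reworded repeat in one child is counted again

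*Protocol*

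**What the plan says.** Protocol section 10.5.6 (Safety Analyses) uses the verbatim term in three places:

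- Classification: "AEs will be classified by system organ class and verbatim term".
- Summary: "AEs will be listed and summarized by treatment group, verbatim term, severity, seriousness, and relationship to study drug".
- De-duplication: it covers "multiple occurrences of the same AE with the same verbatim term in one subject, the AE will be counted once as the worst occurrence".

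The same section also has coarser outputs. It tabulates, per treatment group, the incidence of all AEs and of treatment-related AEs. It adds a class-level table: "The incidence of AEs will be tabulated by system organ class and" treatment group.

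On where the wording comes from, section 8.1.1 states: "All AEs either observed by the investigator or reported by the subject will be recorded regardless of causality". The only instruction that steers wording towards a diagnosis is in section 8.1 and is limited to laboratory findings: "If clinically significant laboratory values lead to or are associated with clinical symptom(s), the diagnosis should be reported as an AE". No preferred term, coding dictionary or grouping of synonyms appears in section 8, section 10.5.6 or Appendix H, and the protocol does not say how verbatim text is assigned to a system organ class.

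**The concern.** A verbatim term records how someone described an event, not which event it was. Making it the counting unit has two consequences.

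- **Between children.** The same event described in different words occupies several rows. Each row shows fewer children than had the event.
- **Within a child.** The de-duplication rule has two conditions: the same AE and the same verbatim term. Two episodes that everyone agrees are the same AE are merged only if the wording also matches. Otherwise the child is counted twice.

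What is at stake is the readability of the term-level safety table from a study meant to inform the design of later trials of this device. A modest cluster of one event could appear as several isolated reports, and the total number of AEs would depend partly on vocabulary. This is a rule that the protocol states, not a detail left open. A statistical analysis plan that coded the terms would be departing from the protocol's own counting unit.

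**Working it through.** The protocol gives no AE rate or AE count, so there is no figure of its own to reproduce. The check applies the counting rule as written.

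**Inputs**

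| Input | Value | Source |
|---|---|---|
| Unit of term-level summary | verbatim term | section 10.5.6 |
| Condition for merging repeats | same AE and same verbatim term, within one subject | section 10.5.6 |
| Children, N | at most 20 | section 10.1 |
| Children with the event, k | 3, 4 or 6 | assumption |
| Equally likely wordings, W | 1, 2, 3 or 4 | assumption |
| Affected children with two episodes | half | assumption |

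**Step 1: a literal example.** Suppose four of 20 children have the same local irritation. Children 1 and 2 are recorded as *nasal irritation*, child 3 as *sore nose* and child 4 as *red nostrils*. Grouped, this is one row of 4/20 = 20%. By verbatim term it is three rows: 2/20 = 10%, 1/20 = 5% and 1/20 = 5%. If child 1 has a second episode recorded as *sore nose*, the rule does not merge it, and five AEs are counted instead of four.

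**Step 2: splitting between children.** With one episode per child, the expected rate per row is k/(W × N). The chance that all k children land in one row is W × (1/W)^k.

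| k | Grouped rate | Expected row rate, W = 2 | Expected row rate, W = 3 | All in one row, W = 2 | All in one row, W = 3 |
|---|---|---|---|---|---|
| 3 | 15% | 7.5% | 5% | 25% | 11.1% |
| 4 | 20% | 10% | 6.7% | 12.5% | 3.7% |
| 6 | 30% | 15% | 10% | 3.1% | 0.4% |

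These are averages over rows, and the largest row is less diluted. For k = 4 and W = 2, the splits 4–0, 3–1 and 2–2 have probabilities 2/16, 8/16 and 6/16. The largest row therefore averages (4 × 2 + 3 × 8 + 2 × 6)/16 = 2.75 children, or 13.75%, against 20% when grouped.

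**Step 3: repeats within a child.** For a child with two episodes worded independently, the second escapes the merge with probability 1 − 1/W. If half of the affected children have two episodes, the expected count per affected child is 1 + 0.5 × (1 − 1/W). The excess over the correct count of one is:

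| W | 0.5 × (1 − 1/W) |
|---|---|
| 1 | 0% |
| 2 | 25% |
| 3 | 33.3% |
| 4 | 37.5% |

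**Step 4: what the rule leaves alone.** A table of children with any AE counts a child once, however many wordings are used. A class-level table that counts children is also unchanged if all synonyms go to the same class. In the example it would change only if, say, *red nostrils* were put in a skin class and *sore nose* in a respiratory class.

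**The case against.** The case for leaving the text alone has real force.

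1. **Section 10.5.6 has other tables.** Incidence of any AE and by class is also given. This stands, read as counts of children, and it confines the problem to the term-level rows and the number of AEs. A reader might infer that AE incidence as a whole is understated. The protocol does not support that.
2. **The main physiological signals do not depend on AE wording.** SpO₂ and transdermal CO₂ are recorded every 15 minutes, blood gases and lactate are taken at the end of each period, and all are summarized numerically. This stands. A reader might infer that desaturation or CO₂ retention with the device would be hidden. That is not shown. Repeated desaturation is also a weak example, because section 8.1.5 and Appendix H withdraw a child whose SpO₂ falls below 90% on oxygen, so only milder drops could normally recur within the study.
3. **The percentages rest on assumptions.** The protocol gives no event rate, episode count or variety of wording. Independent wording of two episodes in one child, within about two hours at one site with ongoing form review, is close to a worst case. This stands.
4. **Nothing ties the 10-patient report to this table.** Appendix H asks whether AE rates match what was assumed beforehand, but it does not say that the verbatim-term table is used, and the protocol gives no numerical assumption. The stopping criteria rest on judgment, with no AE-count threshold. A reader might infer that the interim decision could be misled; the text does not establish that.
5. **Coding belongs in the analysis plan.** This stands only in part. Silence on a dictionary would be no finding, but the protocol goes further and names the verbatim term as the unit.
6. **The listing can be grouped by eye.** True for at most 20 children. However, the protocol does not plan such grouping, and in an open-label study it would be done after the results and the device are known.

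**Conclusion.** The point holds for the term-level AE summary and the once-per-subject rule in section 10.5.6. When the same event is worded differently, term-level rows are split between children, and a reworded repeat in one child is counted again. Per-child incidence of any AE is unaffected, and so is class-level incidence when synonyms share a class.

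The direction follows from the text; the size does not. It is zero if wording is consistent. The 25% excess for two wordings requires that half of the affected children have two episodes and that each episode is worded independently and with equal probability. With at most 20 children, about two hours of observation each and full listings, the practical effect is minor. The change is worth making because the stated rule is the wrong unit and the correction costs almost nothing.

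**What to change.** In section 10.5.6, replace the verbatim term by a coded term wherever AEs are classified, summarized or de-duplicated:

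- Assign every verbatim description to one coded term: either a standard dictionary preferred term or an entry on a short list fixed before analysis.
- Have the assignment made without reference to the device in use when the event occurred.
- Count each child once per coded term, at the worst severity.
- Keep the verbatim text beside the coded term in the listings, so that any grouping can be checked.

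The cost is a wording change in one section and a small amount of coding for at most 20 children. No new data are needed, and no other analysis changes.

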APPENDIX H Data and Safety Monitoring Plan

A. Confidentiality

- 1. Protection of Subject Privacy— During this study, a physical examination and blood tests will be performed. Data will be kept in strict confidence. No information will be given to anyone without permission from the parents of the participant. This statement guarantees confidentiality. Confidentiality is assured by use of study identification numbers. All clinical and laboratory data will be identified only by the study identification number unique to the subject. No participant specimens will be stored for future use.
- 2. Database Protection— The database is secured with password protection. The informatics manager receives only coded information, which is entered into the database under those identification codes. Electronic communication with outside collaborators involves only unidentifiable information.
- 3. Confidentiality during Adverse Event Reporting— Adverse event reports will not include subject-identifiable material. Each will include the study identification number only.

B. Adverse Event Information

1. Definitions- An adverse event (AE) will be defined as **any** new unfavorable or unintended sign, symptom, or disease or change of an existing condition, which occurs during or within 1 hour after treatment, whether or not considered treatment-related. If clinically significant laboratory values lead to or are associated with clinical symptom(s), the diagnosis should be reported as an AE. Lack of treatment effect is not an adverse event in clinical trials because the purpose of the clinical trial is to establish (or evaluate for) a treatment effect.

A serious adverse event (SAE) is defined as an AE that suggests a significant hazard or side effect, regardless of the relationship to study treatment. An SAE includes, but may not be limited to, any event that:

- Results in death.
- Is life-threatening. This definition implies that the subject, in the view of the investigator, is at immediate risk of death from the event. It does not include an event that, had it occurred in a more serious form, might have caused death.
- Requires inpatient hospitalization or prolongs existing hospitalization.
- Results in persistent or significant disability/incapacity.
- 2. Classification of AE Severity AEs will be labeled according to severity, which is based on their impact on the patient, per this Event Grading Scale:

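### Section 10.5.6 applies parallel-group adverse-event rules to a two-period crossover, so its tables cannot give clean counts by device, and the protocol's adverse-event windows disagree

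*Protocol*

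**What the plan says.** **Tabulation.** Section 10.5.6 states: "The incidence of all reported AEs and treatment-related AEs will be tabulated by treatment group". Neither it nor Section 10.5.1 says whether treatment group means the randomized sequence (Group A or B) or the device.

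**Repeat events.** The same section says "In the event of multiple occurrences of the same AE with the same verbatim term in one subject, the AE will be counted once". It then settles which record is kept: "the AE will be counted once as the worst occurrence". The rule mentions neither period nor device.

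**Windows.** Four statements bear on when an event counts:
- Section 8.1 defines an AE as an event "which occurs during or after treatment, whether or not considered treatment-related", with no end.
- Appendix H, part B.1, defines it as one "which occurs during or within 1 hour after treatment, whether or not considered treatment-related".
- Section 8.1.1 says "Adverse event information will be collected through the study period". The synopsis ends the study with Period 2, after about 2 hours, and Appendix A schedules AE recording in Periods 1 and 2 only.
- Section 10.5.6 adds: "Treatment-emergent AEs are defined as AEs occurring after the first initiation of treatment until completion of treatment".

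**Period 2 list.** Section 4.2.2.2 lists the Period 2 procedures without AE or concomitant-medication recording. The synopsis and Appendix A include both.

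**The concern.** Sections 3 and 4.1 say the study should inform trials of the safety of reservoir plus cannula against cannula alone. Section 7.2 gives each child both. A safety table then has to separate events by the device in use, and a child with the same event in both periods has to appear under both. Section 10.5.6 reads as if each child had one treatment. A definitive trial designed from such tables would start from AE incidences that are either pooled over devices or dependent on which occurrence was graded worse. The review after 10 children (Section 10.5.7 and Appendix H, part D) also asks about harm and AE rates.

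The windows matter for another reason. A tabulation rule can be repaired from the listings, but events in an hour when nobody was asked to record them cannot be recovered.

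**Working it through.** The protocol states no AE rate, power or calculated sample size for this point, so there is no figure to reproduce. The check compares the two readings and then shows the possible size under stated assumptions.

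**1. The two readings of treatment group**

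| Reading | What the AE table shows | Consequence |
|---|---|---|
| Sequence (Group A or B) | Each column holds one hour on each device | No comparison of devices |
| Device | A term repeated in one child is kept once, at its worst | An event on both devices is credited to one; equal grades have no rule |

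Section 10.5.4 summarizes baseline characteristics by treatment group, which in a crossover makes sense only by sequence. That favours the first reading without settling it.

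**2. Possible size under the device reading**

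Inputs: n = 20 (Section 10.1, the maximum). Incidence per device p and recurrence probability c are assumptions.

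- Children affected per device = n × p.
- Children affected on both = n × p × c.
- Largest share one device can lose = (n × p × c) / (n × p) = c.

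With p = 20% and c = 50%: 20 × 0.20 = 4 per device, and 4 × 0.50 = 2 on both. If all kept records fall on one device, the other shows 4 − 2 = 2. If they split evenly, each shows 4 − 1 = 3.

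With independent 20% risks, c = 20%: 20 × 0.20 × 0.20 = 0.8 of the 8 expected child-by-device events is removed, or 10%. Over an assumed c of 5% to 80%, the largest loss for one device is 5% to 80%.

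With unequal assumed rates (reservoir 30%, cannula 10%, every cannula event also seen on the reservoir), the true counts are 6 and 2. They become 6 and 0 if the reservoir record is always kept, or 4 and 2 if the cannula record is. The distortion can therefore run in either direction.

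**3. The treatment-emergent cut-off**

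With 20 children at 1:1 there are 10 per sequence.

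| Hour after | Inside the window | Outside the window |
|---|---|---|
| Reservoir | 10 (Group A, its Period 2) | 10 (Group B) |
| Cannula | 10 (Group B, its Period 2) | 10 (Group A) |

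Each device loses 10 of its 20 follow-on hours. The chance of at least one event in 10 uncovered hours is 1 − (1 − q)^10, which is 18%, 40%, 65% and 89% for assumed rates q of 2%, 5%, 10% and 20% per child-hour.

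**4. The windows side by side**

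Section 8.1 never closes and Appendix H closes 1 hour after treatment. Section 8.1.1, the synopsis and Appendix A stop collection at the end of Period 2. Appendix H therefore defines AEs in an hour with no scheduled collection.

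**The case against.** The two faults in Section 10.5.6 cannot both occur. If treatment group means sequence, there is no device column for an event to vanish from. If it means device, a sensible analyst could apply the once-only rule within each column. This stands: what is certain is that the term is undefined and that the rule, as written, suits neither reading. The text does not state the sensible version.

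No recorded data are lost. All AEs are to be recorded and listed, and with at most 20 children the counts by device could be rebuilt. This stands for Periods 1 and 2, but not for the hour after Period 2.

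A reader might infer that the cut-off hides late reservoir harm, because Group B's post-reservoir hour is excluded. The documents do not support that. Group A loses its post-cannula hour in the same way, the cut-off limits only a treatment-emergent set to which no table is assigned, and Section 10.5.6 tabulates all reported AEs. Group A's covered post-reservoir hour is also spent on the cannula, so events there need an attribution rule.

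A reader might also infer from Section 4.2.2.2 that AEs go unrecorded in Group B's reservoir hour. The synopsis, Section 8.1.1 and Appendix A all require recording then, so the omission is editorial.

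Finally, this is a feasibility study with descriptive summaries, and a statistical analysis plan could refine the counting. That lowers the stakes, but the protocol has itself fixed a rule that does not fit its design.

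**Conclusion.** The point holds in a limited form. The AE tables in Section 10.5.6 either pool the two devices or credit an event seen on both to only one, and equal grades have no rule. Separately, the definition and collection windows contradict each other.

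The protocol does not allow the size to be fixed. The illustration of 2 affected children instead of 4 rests on an assumed 20% incidence and 50% recurrence, with every kept record on the other device. A more extreme contrast, such as 20% against 0%, needs complete recurrence with the worse grade on the same device every time. Nothing in the protocol suggests that. No consistent direction of bias is shown, either from the counting rule or from the cut-off.

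**What to change.** In Section 10.5.6:
- Tabulate AEs by the device in use at onset.
- Count each term once per child per device, at the worst occurrence within that device.
- Use as denominator the children who started that device.
- Flag onsets after a switch. Attribute any onset after Period 2 to the last device used, and list it separately.

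Elsewhere, state one AE definition and one collection window, and use them in the synopsis, Sections 8.1, 8.1.1 and 10.5.6, and Appendices A and H. Align the Period 2 list in Section 4.2.2.2 with the synopsis and Appendix A.

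The cost is slightly more tabulation work. If the 1-hour window in Appendix H is kept, it also means one more hour of AE capture in children who are already inpatients, with matching changes to the schedule and the stated study duration.
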